## 7 INTRODUCTION

### 7.1 Background

#### 7.1.1 Gout

Gout affects approximately 4% of the United States population, is the most common form of inflammatory arthritis in men, and is associated with decreased quality of life (Saag and Choi, 2006; Singh and Strand, 2008; Zhu et al., 2011; Sattui et al., 2014). The frequency of gout is increasing worldwide, with prevalence rates estimated to be as high as 7% in older men (Mikuls et al., 2005; Saag and Choi, 2006; Roddy and Doherty, 2010). While the exact prevalence is unknown, as many as 200,000 persons in the United States experience chronic symptoms of gout, which is sometimes referred to as chronic refractory gout, despite trials of oral urate-lowering therapy. This condition is characterized by ongoing symptoms of active disease and a failure to control/maintain serum uric acid (sUA) <6 mg/dL with conventional xanthine oxidase inhibitors (i.e., allopurinol and febuxostat) and uricosuric agents (i.e., probenecid) (Brook et al., 2010; Wertheimer et al., 2013; Khanna et al., 2016). These patients often have significant, disabling urate deposits in soft tissues and bone known as tophi.

Gout and hyperuricemia (defined as a serum uric acid level >6.0 mg/dL [Kidney Disease: Improving Global Outcomes {KDIGO} Guidelines, 2009]) are major problems in the population of kidney transplant recipients. The prevalence rate of 13.1% for gout in the kidney transplant recipient population is approximately 12-fold higher than the prevalence rate for gout in the general non transplanted US population ( $p < 0.0001$ ) (Brigham et al., 2018). Potential contributors to greater disease severity in gout patients with kidney transplants are reduced urate excretion due to renal impairment and reduced utilization of key urate lowering therapies leading to poorer gout control. It is also possible that increased gout severity leads to greater risk of renal failure and hence, the need for transplantation, consistent with evidence of hyperuricemia and gout as risk factors for chronic kidney disease and end-stage renal disease (Radeck et al., 2018). Managing gout in kidney transplant recipients is challenging as it is complicated by serious underlying diseases and by drug regimens needed to treat these conditions and to prevent graft rejection (Stamp et al., 2005). Some immunosuppressive drugs increase uric acid and many conventional urate lowering therapies are potentially contraindicated in kidney transplant recipients.

#### 7.1.2 Pegloticase

[REDACTED]

Two replicate pivotal Phase 3 studies for pegloticase were undertaken to establish the efficacy and safety of the product. The primary endpoint was defined as plasma uric acid (pUA) (highly correlated to serum uric acid) reduction to below 6 mg/dL for 80% of the time in Months 3 and 6 combined. The pooled response rate for pegloticase 8 mg every two weeks was 42%, versus a placebo response rate of 0%. There was also a greater reduction in complete resolution of  $\geq 1$  tophus in the every 2 weeks dosing group, and favorable effect of pegloticase treatment in the reduction of the number of tender and swollen joints. In subsequent open-label extension studies, pegloticase led to continued control of pUA, reduction in gout flares, and continued resolution of tophi, suggesting continuing benefit with extended pegloticase treatment beyond the initial 6 months of therapy, particularly in subjects who met responder criteria in the placebo-controlled trials.

In the Phase 3 pivotal studies, deaths, AEs, SAEs, as well as laboratory abnormalities were generally equally distributed across placebo and pegloticase treatment groups, with the clear exception of gout flares and infusion reactions (IRs). Pegloticase-treated subjects exhibited a higher rate of gout flares during Months 1-3 as uric acid was being acutely lowered, then a decrease in gout flares vs. placebo during Months 4-6. Despite use of prophylactic medications against hypersensitivity including administration of corticosteroids, antihistamine, and acetaminophen in advance of each pegloticase infusion, IRs were seen in 22/85 (26%) of subjects receiving the 8 mg 2 week regimen. There was no specified definition of anaphylaxis in the Phase 3 protocols, and there were no investigator-reported events of anaphylaxis in the Phase 3 studies with pegloticase.

However, in a post-hoc review applying the National Institute of Allergy and Infectious Diseases/ Food Allergy and Anaphylaxis Network (NIAID/FAAN) criteria ([Sampson et al., 2006](#)), it was determined that across the Phase 2 and Phase 3 program, anaphylaxis occurred in 6.5% of subjects treated with pegloticase dosed every 2 weeks. Anaphylaxis generally occurred within 2 hours after treatment. Manifestations included wheezing, peri-oral or lingual edema, or hemodynamic instability, with or without rash or urticaria. All of these events had relatively rapid resolution with the cessation of infusion.

In a post-hoc analysis, the apparent role of immunogenicity in both loss of urate lowering effect and incidence of IRs was appreciated. Only 2% of subjects with anti-pegloticase antibody titers exceeding 1:2430 maintained a urate-lowering response to pegloticase compared with 63% of subjects who were treated for at least 2 months without developing high-titer antibodies ( $p < 0.001$ ) ([Sundy et al., 2011](#)). The incidence of IRs was higher among subjects who developed high-titer antibodies compared with those who had titers that did not exceed 1:2430 (60% vs. 19%;  $p < 0.001$ ) ([Sundy et al., 2011](#)). In addition, most IRs occurred when sUA levels were greater than 6 mg/dL. Retrospective analyses showed that the loss of urate-lowering efficacy, as reflected by sUA of greater than 6 mg/dL, preceded a patient's first IR, whenever it occurred, in 20 (91%) of 22 subjects treated with pegloticase every 2 weeks.

Therefore, discontinuation of pegloticase therapy in subjects who lose urate-lowering response offers a valuable approach for mitigating the risk of IR. A post-hoc analysis of the biweekly pegloticase dosing group in the randomized controlled trials (RCTs) illustrated the impact of several possible stopping rules based on sUA levels. A stopping rule based on 2 consecutive pre-infusion sUA

measurements of greater than 6 mg/dL would have significantly reduced the risk of IR (from 26% to 8%), while having little effect on the treatment response rate (from 42% to 41%) (Keenan et al., 2019). Early post-approval safety surveillance in the US using the stopping rules demonstrated a 69% reduction in the rate of IRs compared with the IR rate recorded during the RCTs (Malamet et al., 2013).

Reducing anti-drug antibodies (ADA) with concomitant administration of the immunomodulatory agent methotrexate (MTX) has been shown to be useful with other infused products that lead to immunogenicity, such as infliximab, in the setting of rheumatoid arthritis treatment. In a recent, prospective, proof-of-concept case series, nine patients with refractory tophaceous gout were pre-treated with MTX prior to co-administration of MTX with KRYSTEXXA. All nine patients were responders as defined by maintaining a serum uric acid at goal of <6 mg/dL for greater than 80% of the observation period, which ranged from 4.5 to

9 months on therapy. No unexpected adverse effects were reported with this coadministration (Botson and Peterson, 2018).

Inherent in organ transplantation is the need for immunosuppression to maintain the viability of the transplant, and prevent rejection. There are no formal clinical trials of uricases, including pegloticase, in kidney transplant recipients with gout, although pegloticase has been used successfully in a small number of transplant recipients. Hershfield et al. (2014) reported a trial of pegloticase administered as 8 mg intravenously (IV) every three weeks for up to 5 infusions to 30 patients, including 7 kidney transplant recipients, with refractory gout who were receiving immunosuppression with various combinations of mycophenolate mofetil, cyclosporine, tacrolimus, and azathioprine (AZA). Five of the 7 transplant recipients responded well to pegloticase, and only 1 of 7 developed antibodies to pegloticase, compared to 9 of

20 pegloticase-naïve non-transplant recipients who were not on immunosuppressives. Of the two transplant recipients who did not respond well to pegloticase, one discontinued at the time of the second infusion with an unrelated SAE (duodenal ulcer which caused loss of the pancreatic graft), and the other discontinued after the third infusion with an unrelated SAE (myocardial infarction); the subject with the myocardial infarction was also the one transplant recipient who developed anti-pegloticase antibodies.

### 7.1.2.1 Physicochemical Properties

[REDACTED]

[REDACTED]

[REDACTED]

[REDACTED]

### 7.1.2.3 Non-clinical Pharmacokinetics

[REDACTED]

[REDACTED]

[REDACTED]

[REDACTED]

### 7.1.2.4 Clinical Pharmacokinetics

[REDACTED]

[REDACTED]

[REDACTED]

[REDACTED]

[REDACTED]

[REDACTED]

### 7.1.2.5 Risks of Pegloticase

[REDACTED]

- [REDACTED]
- [REDACTED]
- [REDACTED]
- [REDACTED]

[REDACTED]

[REDACTED]

[REDACTED]

[REDACTED]

[REDACTED]

[REDACTED]

## 7.2 Rationale for this Study

During the pre-marketing Phase 3 studies for pegloticase, subjects with organ transplant were excluded from participation; however, subjects with renal impairment were included, and showed comparable safety and efficacy as the general study population. Kidney transplant recipients with uncontrolled gout have the potential to benefit from the ability of pegloticase to rapidly deplete urate deposits, even when urate excretion is impaired. In addition, immunosuppressive agents to prevent rejections have the potential to thwart the formation of ADA against pegloticase, thereby preserving its effectiveness and decreasing the risk of infusion reactions.

This study will test safety and effectiveness of pegloticase 8 mg administered intravenously every 2 weeks in kidney transplant subjects with chronic gout refractory to conventional urate lowering therapy (ULT). Prospective use of sUA stopping rules, with pegloticase treatment cessation (but study continuation) when a subject has a pre-infusion sUA level >6 mg/dL on two consecutive study visits, will also help confirm the value of this approach to reduce IR risk.

## 7.3 Rationale for Dose Selection

[REDACTED]

## 8 STUDY OBJECTIVES

The overall objective of the study is to assess the efficacy and safety of pegloticase in kidney transplant subjects with uncontrolled gout refractory to conventional urate lowering therapy.

### Primary Objective:

To evaluate the effect of pegloticase on the response rate of sustained serum uric acid (sUA) reduction to sUA <6 mg/dL during Month 6 of treatment.

### Secondary Objectives:

- To evaluate the effect of pegloticase on the response rate of sustained serum uric acid reduction to sUA <5 mg/dL during Month 6 of treatment;
- To evaluate the effect of pegloticase on pain assessed by the Health Assessment Questionnaire (HAQ) pain score; and
- To evaluate the effect of pegloticase on disability assessed by the Health Assessment Questionnaire - Disability Index (HAQ-DI) score.

### Exploratory Objectives:

- [REDACTED]
- To evaluate the pharmacokinetics (PK) of pegloticase and the profile of anti-methoxy-poly(ethylene glycol) (PEG) and anti-uricase IgG antibodies; and
- To evaluate the safety and efficacy 3 months after the end of treatment with pegloticase.

### Safety and Tolerability Objectives:

To assess the overall adverse event (AE)/serious AE (SAE) profile including AEs of special interest (AESI) (infusion reactions [IRs], anaphylaxis, gout flares and cardiovascular [CV] events), laboratory tests, vital signs and physical exam, and incidence of biopsy confirmed renal rejection.

## 9 INVESTIGATIONAL PLAN

### 9.1 Overall Study Design and Plan

This is a Phase 4, multi-site, open-label, efficacy and safety study of pegloticase in adult subjects with uncontrolled gout who have undergone kidney transplantation. Twenty subjects will be enrolled.

The study design will include: 1) a Screening Period, lasting up to 35 days; 2) a 24-week treatment period which includes an End-of-Study (Week 24)/Early Termination Visit; 3) a safety follow-up phone/email Visit 30 days after the last infusion; and 4) a 3-month post-treatment follow up visit.

During the Screening Period, eligibility will be confirmed.

Samples for measurement of sUA levels will be collected at the Screening Visit, prior to each infusion, 15-60 minutes after the end of each infusion and at the Week 24/End-of-Study/Early Termination Visit. Additional samples for sUA levels will be collected at non-infusion Visits at Weeks 21 and 23.

Subjects who meet all of the inclusion criteria and none of exclusion criteria during Screening will be enrolled at the Day 1 Visit to receive pegloticase 8 mg administered IV every 2 weeks from Day 1 through Week 22, inclusive. During this 24-week treatment phase, subjects who meet the stopping rule (based on elevated sUA levels, see Stopping Rule in Section 9.5.7.2) or discontinue treatment for any other reason will complete the End-of-Pegloticase-Infusions Visit procedures within 2 weeks and be encouraged to continue to participate in all visits through the end of the study. Subjects will return for regularly scheduled visits and will complete all study visit procedures with the exception of the pegloticase infusion and IR prophylaxis. After the Week 24/End-of-Study/Early Termination Visit (or End-of-Pegloticase-Infusions Visit [if applicable]), subjects should resume regular care for gout per the judgment of the treating physician, including resumption of ULT upon pegloticase discontinuation, if appropriate.

Subjects will have a 3-month Follow-up visit to assess clinical status, including sUA levels.

On days of scheduled infusions, pegloticase will be administered after all pre-dose study visit assessments have been completed. The date and start and stop times of infusion will be recorded. The date of the first dose of pegloticase is defined as Day 1. All subsequent doses and study visits will be scheduled based on the Day 1 Visit date.

It is required that before a subject begins the treatment period, he or she has been taking protocol defined standard gout flare prophylaxis (i.e., colchicine initial dose 0.3 to 0.6 mg/day if tolerated and low-dose prednisone  $\leq$  10 mg/day); for subjects already taking chronic corticosteroids, colchicine 0.3 to 0.6 mg/day should be added. In subjects with eGFR  $\leq$  30 mL/min/1.73m^2, the dose of colchicine should not be more than 0.3 mg/day. In subjects taking cyclosporine, only low dose prednisone (and not colchicine) should be used for  $\geq$  1 week before the first infusion. Gout flare prophylaxis should continue for the duration of the 24-week treatment period. Subjects should be monitored closely for

symptoms of colchicine excess during the study. Reductions in dose, dose frequency or discontinuation of colchicine are permitted if not tolerated.

For IR prophylaxis, fexofenadine (60 or 180 mg orally) will be taken the day before each infusion; fexofenadine (60 or 180 mg orally) and acetaminophen (1000 mg orally) will be taken the morning of each infusion. In addition, methylprednisolone (125 mg IV from Day 1 to Week 10 and 80 mg IV from Week 12 until the end of treatment) is recommended to be administered over an infusion duration between 10 and 30 minutes, immediately prior to each pegloticase infusion. Alternate IV corticosteroid regimen may be substituted for methylprednisolone at the discretion of the Investigator. The dose of fexofenadine should be 60 mg orally unless in subjects with decreased renal function and 180 mg orally in subjects with normal renal function ( $eGFR > 90 \text{ mL/min/1.73m}^2$ ).

Serum samples for PK analysis of pegloticase will be collected approximately 15 minutes to 2 hours after the end of infusion on Day 1, prior to the infusion and approximately 15 minutes to 2 hours after the end of infusion at Weeks 2, 6, 14 and 22. An additional PK sample will be collected at the Week 21 Visit, End-of-Pegloticase-Infusions Visit (if applicable) and Week 24/End of Study/Early Termination Visit.

Serum samples for evaluation of anti-PEG and anti-uricase IgG antibodies will be collected prior to the infusion on Day 1 and prior to the infusions at the Weeks 2, 6, 14 and 22. An additional sample will be collected at each of the End-of-Pegloticase-Infusions Visit (if applicable),

[figure not shown]
Week 24/End-of-Study /Early Termination Visit and the 3-month follow up visit. In the event of an AE suspected to be an IR, a sample will be collected at that time or at the subsequent visit for future evaluation of ADAs.

Safety assessments, including monitoring and recording of all AEs, whether or not drug-related, measurement of vital signs, physical examinations, and monitoring of hematology and blood chemistry and acute renal rejection, will be performed.

An independent external adjudication committee will review reported events of IRs, major CV events and anaphylaxis.

An overview of the study design is presented in the schematic below, and details of study activities are provided in Section 2.1.

Figure 9.1 Schematic of Study Design

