It is required that before a subject begins the treatment period, he or she has been taking protocol defined standard gout flare prophylaxis (colchicine at initial dose of 0.3 to 0.6 mg/day if tolerated and low-dose prednisone  $\leq$  10 mg/day; for subjects already taking chronic corticosteroids, only colchicine 0.3 to 0.6 mg/day should be added. In subjects with  $eGFR \leq 30$  mL/min/1.73m^2, the dose of colchicine should not be more than 0.3 mg/day. In subjects taking cyclosporine, only low dose prednisone (and not colchicine) should be used for  $\geq$  1 week before the first infusion. Gout flare prophylaxis should continue for the duration of the 24-week treatment period. Subjects should be monitored closely for symptoms of colchicine excess during the study. Reductions in dose, dose frequency or discontinuation of colchicine are permitted if not tolerated.

For Infusion Reaction (IR) prophylaxis, fexofenadine (60 or 180 mg orally) will be taken the day before each infusion; fexofenadine (60 or 180 mg orally) and acetaminophen (1000 mg orally) will be taken in the morning before each infusion. In addition, methylprednisolone (125 mg IV from Day 1 to Week 10 and 80 mg IV from Week 12 until the end of treatment) is recommended to be administered over an infusion duration between 10 and 30 minutes, immediately prior to each pegloticase infusion. Alternate IV corticosteroid regimen may be substituted for methylprednisolone at the discretion of the Investigator. The dose of fexofenadine should be 60 mg orally in subjects with decreased renal function and 180 mg orally in subjects with normal renal function ( $eGFR >90$  mL/min/1.73m^2).

Serum samples for PK analysis of pegloticase will be collected approximately 15 minutes to 2 hours after the end of infusion on Day 1, prior to the infusion and approximately 15 minutes to 2 hours after the end of infusion at Weeks 2, 6, 14 and 22. An additional PK sample will be collected at the Week 21 non-infusion visit,

End-of-Pegloticase-Infusions Visit (if applicable) and End-of-Study/Early Termination Visit.

Serum samples for evaluation of anti-PEG and anti-uricase immunoglobulin G (IgG) antibodies will be collected prior to the infusion on Day 1 and prior to the infusions at the Weeks 2, 6, 14 and 22. An additional sample will be collected at the End-of-Pegloticase-Infusions Visit (if applicable), End-of-Study/Early Termination Visit and the

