9. Electrocardiogram should be completed during Screening. The electrocardiogram is read at the site. If a subject experiences an AE suspected to be an IR, a 12-lead ECG will also be performed.
10. AEs/SAEs will be collected from the time of signature of the ICF until the 3-month Post-Treatment Follow-up Visit. For each AE, the Investigator will be asked to record if the event was possibly an infusion reaction or anaphylaxis and if so, will be prompted to complete additional eCRFs.
11. [REDACTED]

13. Subjects are required to take at least one protocol standard gout flare prophylaxis (i.e., colchicine initial dose 0.3-0.6 mg/day and low-dose prednisone  $\leq 10$  mg/day); for subjects already taking low dose corticosteroids, colchicine 0.3-0.6 mg/day should be added. In subjects with  $eGFR \leq 30$  mL/min/1.73m^2, the dose of colchicine should not be more than 0.3 mg/day. In subjects taking cyclosporine, only low dose prednisone (and no colchicine) should be used for  $\geq 1$  week before the first infusion. Gout flare prophylaxis should continue for the duration of the 24-week treatment period. Subjects should be monitored closely for symptoms of colchicine excess during the study. Reductions in dose, dose frequency or discontinuation of colchicine are permitted if not tolerated.
14. For IR prophylaxis, fexofenadine (60 - 180 mg orally) will be taken the night before each infusion.
15. IR prophylaxis includes fexofenadine administered the day before each infusion; fexofenadine and acetaminophen (1000 mg orally) administered on the morning of each infusion. In addition, methylprednisolone (125 mg IV from Day 1 to Week 10 and 80 mg IV from Week 12 until the end of treatment) is recommended to be administered over an infusion duration between 10 and 30 minutes, immediately prior to each pegloticase infusion. Alternate IV corticosteroid regimen may be substituted for methylprednisolone at the discretion of the Investigator. The dose of fexofenadine should be 60 mg orally in subjects with decreased renal function and 180 mg orally in subjects with normal renal function ( $eGFR >90$  mL/min/1.73m^2).

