### 9.3 Selection of Study Population

#### 9.3.1 Inclusion Criteria

Eligible subjects must meet/provide **all** of the following criteria:

1. Willing and able to give informed consent;
2. Willing and able to comply with the prescribed treatment protocol and evaluations for the duration of the study;
3. Adult men or women  $\geq 18$  years of age;
4. Is a recipient of a de novo kidney from a living or deceased donor and is  $>1$  year post-transplant prior to screening;
5. Is on a stable standard of care immunosuppression therapy for at least 3 months prior to screening;
6. Kidney allograft is functional at entry, based on an estimated GFR (eGFR)  $\geq 15$  mL/min/1.73m^2;
7. Women of childbearing potential have a negative screening serum pregnancy test and will be required to use a medically approved form of birth control during their participation in the study;
8. Uncontrolled gout, defined as:
  - A. Hyperuricemia during screening as documented by sUA  $\geq 7$  mg/dL during Screening and prior to entry into the Treatment Period (Note: the sUA may be repeated up to 3 times during the Screening Period to confirm eligibility); and
  - B. Inability to maintain sUA  $<6$  mg/dL on other urate-lowering therapy or intolerable side effects or contraindicated with conventional urate-lowering therapy; and
  - C. At least 1 of the following:
    - i. Evidence of tophaceous deposits;
    - ii. Recurrent gout flares defined as 2 or more flares in the past 12 months prior to Screening;
    - iii. Presence of chronic gouty arthritis; and
9. Able to tolerate low-dose prednisone ( $<10$  mg/day) as part of the required standard gout flare prophylaxis regimen for  $\geq 1$  week before the first infusion.

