#### 9.4.1.2 Infusion Reaction Prophylaxis

Since IRs can occur with pegloticase, all subjects will receive IR prophylaxis prior to each infusion, consisting of an antihistamine, acetaminophen, and a corticosteroid. To standardize this regimen, subjects will receive fexofenadine (60 or 180 mg orally) the day before each infusion; fexofenadine (60 or 180 mg orally) and acetaminophen (1000 mg orally) the morning of each infusion. In addition, methylprednisolone (125 mg IV from Day 1 to Week 10 and 80 mg IV from Week 12 until the end of treatment) is recommended to be administered over an infusion duration between 10 and 30 minutes, immediately prior to each pegloticase infusion.

Alternate IV corticosteroid regimen may be substituted for methylprednisolone at the discretion of the Investigator. The dose of fexofenadine should be 60 mg orally in subjects with decreased renal function and 180 mg orally in subjects with normal renal function (eGFR

>90 mL/min/1.73m^2). Substitution of the corticosteroid is not allowed. The name, dose, route, date, and time of administration of each prophylactic medication will be recorded in the medical record and in the eCRF. The methylprednisolone used for IR prophylaxis will be supplied by the site. Other IR medications administered prior to each infusion may also be supplied by the site.

Prescriptions are to be filled at a local pharmacy, as needed. At study visits, the subject will be asked a Yes/No question whether IR prophylaxis was taken per protocol.

As a precaution, emergency equipment will be readily available to treat a possible hypersensitivity reaction, and will include drugs that would be used to treat an anaphylactic reaction. Personnel trained in managing IRs and in the use of the emergency equipment will be readily available during and for 1 hour after the infusion. As IRs can occur after the completion of the infusion, subjects will be observed for 1 hour post-infusion.

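### Protocol Section 9.1 words the fexofenadine renal rule so that subjects with decreased renal function have no stated dose, in conflict with six other statements, and footnote 14 adds a dose range

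*Protocol*

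**What the plan says.** Fexofenadine is part of the infusion-reaction prophylaxis before every pegloticase infusion: one dose the day before and one on the morning itself. Two strengths are named, and the choice depends on renal function.

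- Protocol Section 9.1 first offers the two strengths ("fexofenadine (60 or 180 mg orally) will be taken the day before each infusion") and then gives the rule: "The dose of fexofenadine should be 60 mg orally unless in subjects with decreased renal function and 180 mg orally" for normal renal function, defined as eGFR above 90 mL/min/1.73m².
- Protocol Section 9.4.1.2, the section devoted to this prophylaxis, has: "The dose of fexofenadine should be 60 mg orally in subjects with decreased renal function and 180 mg orally", again with 180 mg for normal function.
- The Synopsis, in both its study-design and dose-regimen parts, agrees with Section 9.4.1.2: the dose "should be 60 mg orally in subjects with decreased renal function and 180 mg orally in subjects with normal renal function". So do footnote 15 of the Section 2.1 schedule, SAP Section 4.1 and footnote 15 of the SAP schedule.
- Footnote 14 of the schedule, in the protocol and repeated in the SAP, reads: "For IR prophylaxis, fexofenadine (60 - 180 mg orally) will be taken the night before each infusion". It carries no renal condition.

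On eligibility, Section 9.3.1 says: "Kidney allograft is functional at entry, based on an estimated GFR (eGFR") of at least 15 mL/min/1.73m². It sets no upper limit.

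**The concern.** Section 9.1 belongs to the investigational plan, so its dosing sentence is an instruction and not background. The clause that goes wrong is the one on decreased renal function, and the trial enrols kidney recipients down to an eGFR of 15.

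Three features of the plan make a single clear rule useful. Section 9.4.1.2 says its purpose is to standardise the regimen. Infusion reactions are an adverse event of special interest and are adjudicated. Sites also record a yes/no answer on whether prophylaxis was taken as the protocol requires, and that answer is well defined only if the protocol has one rule. SAP Section 12.1 presents prophylaxis use in listings only, so dose differences between sites would not appear in any summary table.

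**Working it through.** The plan gives no figure on this point to reproduce. The check compares every fexofenadine dose statement in the two documents.

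**Step 1: full statements of the renal rule.**

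| Place | Decreased function | Normal function (eGFR above 90) | Contains *unless*? |
|---|---|---|---|
| Protocol Synopsis, study design | 60 mg | 180 mg | no |
| Protocol Synopsis, dose regimen | 60 mg | 180 mg | no |
| Protocol Section 2.1, footnote 15 | 60 mg | 180 mg | no |
| Protocol Section 9.1 | excluded from 60 mg; none stated | 180 mg | yes |
| Protocol Section 9.4.1.2 | 60 mg | 180 mg | no |
| SAP Section 4.1 | 60 mg | 180 mg | no |
| SAP schedule, footnote 15 | 60 mg | 180 mg | no |

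There are 5 + 2 = 7 full statements. One contains *unless*; the other 6 agree with each other.

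**Step 2: literal reading of Section 9.1.** The documents put a number on normal function only, so I take decreased to mean eGFR of 90 or below (an assumption).

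- eGFR 90 or below: the *unless* clause takes these subjects out of the 60 mg dose. The 180 mg dose is kept for eGFR above 90. No dose remains.
- eGFR above 90: the 60 mg clause now covers these subjects, and so does the 180 mg clause. Two doses apply.

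The sentence therefore cannot be followed as written in either group.

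**Step 3: footnote 14 against the rest.** The footnote joins 60 and 180 with a dash. The Synopsis and Sections 9.1 and 9.4.1.2 present them as two alternatives. Footnote 15, immediately after, includes the day-before dose and states the renal rule. The two footnotes thus describe the same dose in different ways, one with a renal condition and one without.

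**Step 4: how often the rule is applied.** Two doses per infusion × 12 infusions = 24 doses for a subject who completes treatment, and fewer for anyone who stops early. The two strengths differ by 180 / 60 = 3-fold. These figures describe how often the rule is used and how far apart the strengths are. They do not measure any dosing error that Section 9.1 would cause.

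**Step 5: how many subjects.** The entry criterion is eGFR of at least 15 with no upper limit, and no expected distribution is given. On the criteria alone, anywhere from 0 to 20 of the 20 planned subjects could have eGFR of 90 or below.

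**The case against.** The strongest reply is that this is one stray word and one loose footnote, and that the text sites work from is consistent. Protocol Section 9.4.6.3.1.2 and every infusion-visit procedure list refer to Section 9.4.1.2 for the prophylaxis, and that section has no *unless*. Section 9.1 itself refers to Section 2.1 for details of study activities, where footnote 15 states the same rule as Section 9.4.1.2. No fexofenadine instruction in the visit procedures points to Section 9.1. Section 9.4.1.2 also requires the name, dose, route, date and time of each prophylactic drug in the eCRF, so with about 20 subjects the listings would show what each received.

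Most of that stands, and it limits the practical reach. It does not remove the contradiction: the documents contain no clause saying which section prevails, and Section 9.1 is current text.

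Three stronger readings are tempting, and the documents do not support them:

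- A reader might infer that Section 9.1 reverses the rule and gives 180 mg to subjects with decreased function. It does not. The 180 mg clause is unchanged; only the 60 mg clause is garbled, most likely a drafting remnant.
- A reader might infer that footnote 14 leaves the dose open. Read with footnote 15, it does not.
- A reader might infer that most enrolled subjects are affected. That is plausible for transplant recipients, but no eGFR distribution is given to support it.

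**Conclusion.** The contradiction is real and minor. One of seven full statements of the rule conflicts with the other six and, read literally, gives subjects with decreased renal function no dose. In both documents, footnote 14 writes a range where other places give two alternatives. The conflict concerns a premedication instruction that a completing subject meets up to 24 times, but the cross-references to Section 9.4.1.2 make it unlikely that sites would rely on the faulty sentence alone. The share of subjects concerned cannot be derived. The literal reading assumes that decreased function means eGFR of 90 or below. The primary endpoint, the sample size and the confidence interval do not depend on this point. This review takes no view on which dose is right.

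**What to change.** At the next amendment, reconcile Protocol Section 9.1, footnote 14 in the protocol and SAP schedules, and the other statements of the rule. Both documents should then give one rule, in the same words and with the same renal criterion, for the day-before and the morning dose. The sponsor's clinical team should confirm which rule is intended.

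The cost is wording only. If the team confirms the rule in the six agreeing statements, three places change: the Section 9.1 sentence, protocol footnote 14 and SAP footnote 14. If it intends something else, the other statements change too. Protocol Section 9.7 requires a formal amendment with IRB approval, so the edit is best carried with other changes. The analysis is not affected. The gain is a small one in patient safety, together with a clear standard for the yes/no compliance question.
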